7.1 Study-Stop Criteria

The entire study may be discontinued at the discretion of the Sponsor based on the occurrence of the following:

- AEs with respect to their frequency, severity, and/or duration
- Medical or ethical reasons affecting the continued performance of the study
- Difficulties in the recruitment of subjects
- Cancellation of drug development

8 Enrollment Criteria

8.1 Inclusion Criteria

Subjects who meet the following criteria may be included in the study:

1. Males and females 18 to 75 years of age (inclusive) who are able to comprehend and willing to sign an Informed Consent Form (ICF)
2. Histologically confirmed NASH diagnosis as defined by the NIH NASH CRN (see [Appendix 1, Kleiner 2005](#)) and liver biopsy criteria outlined below. A historical biopsy is acceptable if performed within the required 6-months of Screening and tissue slides are available for a qualified central pathologist reader:
 - NAS ≥ 4 with a minimum of 1 point in each component
 - Histologic evidence of Stage 2 or Stage 3 fibrosis without cirrhosis
3. Total liver fat content of $\geq 8\%$ as measured by MRI-PDFF
4. Subjects with T2D or insulin resistance are permitted as long as diabetic medications are stable as outlined in [Section 9.3 Concomitant Medications](#) and subject attempts to maintain a stable regimen during the study period.
5. Other concomitant medications/therapies for NAFLD or NASH: requires a stable regimen for at least 3 months prior to the Screening biopsy of record and throughout the study (Refer to [Section 9.3 Concomitant Medications](#)).
6. Statin use based on the following criteria for statin-naïve or statin-experienced at Screening:
 - **Statin naïve** is defined as no administration of statins within 3 months prior to Screening.
 - **Statin experienced** is defined as administration of the following stable daily doses of approved statin therapies taken for at least 3 months prior to Screening through Week 2
 - Atorvastatin: ≤ 40 mg/day
 - Fluvastatin: ≤ 40 mg/day
 - Lovastatin: ≤ 40 mg/day (immediate release), ≤ 30 mg/day (extended release)
 - Pitavastatin: ≤ 2 mg/day
 - Pravastatin: ≤ 40 mg/day
 - Simvastatin: ≤ 40 mg/day
 - Rosuvastatin: ≤ 20 mg/day

7. The following laboratory parameters must be met at Screening:

- Total bilirubin \leq ULN (Upper Limit of Normal) based on the Day -42 value or average of at least 2 Screening values obtained during the Screening Period, except for subjects with an established diagnosis of Gilbert's Syndrome provided the direct bilirubin level is \leq ULN and hemoglobin and reticulocyte count are normal.
- Aspartate aminotransferase (AST) \geq 30 IU/L and \leq 250 IU/L in all subjects, based on the Day -42 value or average of at least 2 screening values obtained during the Screening Period
 - i. Exception: subjects with an average AST \geq 20 and $<$ 30 IU/L will be permitted provided that at least one of the following criteria are met:
 1. Local historical biopsy within 6 months with a NAS of 4 with at least 1 point in each component and fibrosis Stage 2 or 3. Subjects with a historical biopsy will have their slides evaluated by the central reader prior to undergoing MRI-PDFF.
 2. Vibration-controlled transient elastography (VCTE[®] by Fibroscan) \geq 9.5 kPa within 6 months of Screening. If no historical Fibroscan is available, it may be conducted and evaluated as per local "standard-of-care" prior to Day -28.
- Hemoglobin A1c (HbA1c) \leq 9.5%
- Platelet count \geq Lower Limit of Normal (LLN) (i.e., 140,000/mm³)
- Creatinine clearance \geq 60 mL/min as calculated by Cockcroft-Gault equation
- Alpha fetoprotein (AFP) $<$ 100 ng/mL

8. Female subjects who are of non-childbearing potential must have had a hysterectomy, bilateral oophorectomy, medically documented ovarian failure, are documented postmenopausal, OR a follicle stimulating hormone $>$ 40 mIU/mL

9. Female subjects of child-bearing potential must not be pregnant or nursing. Female subjects of childbearing potential are defined as women $<$ 55 years of age with \leq 2 years of amenorrhea and who meet both of the following criteria:

- i. A negative serum pregnancy test at Screening and urine pregnancy test prior to randomization
- ii. Correct and consistent use of one of the following methods of birth control in addition to a male partner using a condom from Screening to 30 days after the last dose of study drug:
 1. hormone containing contraceptive
 2. intrauterine device with a failure rate $<$ 1% per year
 3. cervical cap or diaphragm with spermicidal agent
 4. tubal sterilization
 5. vasectomy in male partner

6. complete abstinence of sexual intercourse
10. Male subjects are eligible for the study if they meet the following criteria:
 - a. Male subjects must agree to consistently and correctly use a condom in combination with one of the following from the date of consent to 30 days after the last dose of study drug:
 - i. Condom with spermicide
 - ii. Vasectomy
 - iii. Complete abstinence of sexual intercourse.
- AND
- b. Female partner(s) must use any of the approved methods of birth control in inclusion criterion #9.
11. Able and willing to comply with the dosing instructions for study-drug administration and able to complete the study schedule of assessments
12. BMI ≥ 25 kg/m² for subjects self-identified of Asian descent only

8.2 Exclusion Criteria

The following will exclude potential subjects from the study:

1. Clinically significant acute or chronic liver disease of an etiology other than NASH
2. Evidence of drug-induced steatohepatitis secondary to amiodarone, corticosteroids, estrogens, methotrexate, tetracycline, or other medications known to cause hepatic steatosis
3. History or presence of cirrhosis (compensated or decompensated) as determined by histology and/or relevant medical complications and/or laboratory parameters
4. Prior or pending liver transplantation
5. Model of end-stage liver disease (MELD) score ≥ 12 (except for subjects with established Gilbert's syndrome)
6. Evidence of worsening liver disease (defined below) between Screening visits (i.e., Day -42 and Day -28) including measures of AST, ALT, TBL, and ALP:
 - For subjects with AST, ALT, TBL, or ALP baseline levels $>$ ULN on Day -28, the Day -28 assessment should not exceed an increase of 35% over the Day -42 assessment.
 - For subjects with Gilbert's syndrome and a total bilirubin $>$ ULN at the Day -42 assessment, the total bilirubin assessment at Day -28 should not exceed an increase of 50% over the Day -42 assessment.

Note: For AST, ALT, TBL, and ALP, if the percent increase in laboratory values between Day -42 and Day -28 is $> 35\%$, repeat blood samples will be

collected at an unscheduled visit at a minimum of two weeks from the Day -28 visit. The average of Day -42 and Day -28 values will be compared to the 3rd value to determine if eligibility ranges (i.e., % agreement \leq 35%) are met.

7. Clinically significant cardiovascular or cerebrovascular event or new diagnosis within 6 months of Screening, including but not limited to congestive heart failure, myocardial infarction, acute coronary syndrome, revascularization, stroke (hemorrhagic or ischemic), transient ischemic attack (TIA), or implanted defibrillator or pacemaker (except for uncomplicated elective pacemaker procedure, 3 months post procedure will be allowed).
8. History of gastric bypass or bariatric surgery or planned procedure during the study period. Removal of a gastric balloon or lap band is permitted if surgery performed within 6 months prior to Day 1.
9. Type 1 diabetes
10. History of clinically significant unstable or untreated illness or any other major medical disorder that may interfere with patient treatment, assessment, or compliance with the protocol
11. Any contraindication or inability to obtain an MRI
12. Inability to obtain or any contraindication to liver biopsy (if a historical biopsy with viable tissue slides are not available within the required time period)
13. Screening ECG with clinically significant abnormalities or unexplained findings that the investigator feels needs further evaluation and treatment
14. Positive for HBsAg, anti-HIV, or anti-HCV plus HCV-RNA. Subjects who are anti-HCV- positive but HCV-RNA negative (secondary to treatment or viral clearance) are eligible with at least a 1-year period since documented sustained viral response at Week 12 post-treatment
15. History of malignancy diagnosed or treated within 2 years (recent localized treatment of squamous or non-invasive basal cell skin cancers is permitted; cervical carcinoma in situ is allowed if appropriately treated prior to Screening); subjects under evaluation for malignancy are not eligible
16. Clinically-relevant drug use within 12 months of Screening. A positive drug screen will exclude subjects unless it can be clearly explained by a prescribed medication. The diagnosis and prescription must be approved by the Investigator and the Sponsor Medical Monitor or designee. Marijuana is not part of the drug screen.
17. Significant alcohol intake as measured by a phosphatidylethanol (PEth) level \geq 200 ng/mL AND positive results from AUDIT-C alcohol consumption questionnaire ([Appendix 8](#))

18. Criterion eliminated per protocol amendment 3

19. Consumption of \geq 21 units of alcohol per week in males and \geq 14 units of alcohol per week in females for two years prior to enrollment, where a “unit” of alcohol is equivalent to a 12-ounce beer, 4-ounce glass of wine, or 1-ounce shot of hard liquor
20. Use of any prohibited concomitant medications as described in [Section 9.3](#) from Day -42 to the end of the study including:
 - Investigational agents, other than aldafermin, or devices for any indication. These agents must also have been discontinued prior to Screening
 - Combination preparations of statins and other lipid-lowering agents (other than approved statin therapies listed in inclusion criterion #6)
 - Weight loss medications
 - Any medication that is contraindicated according to the rosuvastatin package insert ([Appendix 6](#)) or if subject has a known hypersensitivity to rosuvastatin product components ([Section 10.1.3](#)).
 - Any medication that is contraindicated according to the ezetimibe package insert ([Appendix 7](#)) or if subject has a known hypersensitivity to ezetimibe product components.
 - Hepatotoxic medications ([Appendix 9](#)). For subjects who have been on stable therapy with no related hepatotoxicity, the MM may be contacted to assess the medical context and eligibility of the subject. Allopurinol to treat gout is permitted provided there is no prior history of intolerance.
 - Anabolic steroids; Low levels of estrogen or testosterone as replacement therapy are allowed per Medical Monitor approval.
21. History of statin intolerance as evidenced by presence of ALT elevations, adverse event(s), or other significant side effects attributed to statins
22. Prior participation in a clinical trial of aldafermin is excluded **unless** previously enrolled into a placebo treatment group of the trial.
23. Subject with severe allergic or anaphylactic reactions to recombinant therapeutic proteins, fusion proteins, or chimeric, human, or humanized antibodies
24. Participation in a study of another investigational agent:
 - NASH investigational agents: < 3 months prior to Screening if treated with active study drug or < 28 days if treated with placebo
 - All other investigational agents: within 28 days or five half-lives of the drug (whichever is longer) prior to Screening
25. Any acute or chronic condition that, in the opinion of the Investigator or the Sponsor Medical Monitor, would limit the subject’s ability to complete and/or participate in this clinical study

26. Pregnancy or lactation

27. *Criterion eliminated per protocol amendment 4*

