- 12. $BMI \geq 25 \text{ kg/m}^2$ for subjects self-identified of Asian descent only

Exclusion Criteria

The following will exclude potential subjects from the study:

- 1. Clinically significant acute or chronic liver disease of an etiology other than NASH
- 2. Evidence of drug-induced steatohepatitis secondary to amiodarone, corticosteroids, estrogens, methotrexate, tetracycline, or other medications known to cause hepatic steatosis
- 3. History or presence of cirrhosis (compensated or decompensated) as determined by histology and/or relevant medical complications and/or laboratory parameters
- 4. Prior or pending liver transplantation
- 5. Model of end-stage liver disease (MELD) score ≥ 12 (except for subjects with established Gilbert's syndrome)
- 6. Evidence of worsening liver disease (defined below) between Screening visits (i.e., Day -42 and Day -28) including measures of AST, ALT, TBL, and ALP:
 - For subjects with AST, ALT, TBL or ALP baseline levels $> \text{ULN}$ on Day -28, the Day -28 assessment should not exceed an increase of 35% over the Day -42 assessment.
 - For subjects with Gilbert's syndrome and a total bilirubin $> \text{ULN}$ at the Day -42 assessment, the total bilirubin assessment at Day -28 should not exceed an increase of 50% over the Day -42 assessment.

Note: For AST, ALT, TBL and ALP, if the percent increase in laboratory values between Day -42 and Day -28 is $> 35\%$, repeat blood samples will be collected at an unscheduled visit at a minimum of two weeks from the Day - 28 visit. The average of Day -42 and Day -28 values will be compared

to the 3rd value to determine if eligibility ranges (i.e., % agreement \leq 35%) are met.

7. Clinically significant cardiovascular or cerebrovascular event or new diagnosis within 6 months of Screening, including but not limited to congestive heart failure, myocardial infarction, acute coronary syndrome, revascularization, stroke (hemorrhagic or ischemic), transient ischemic attack (TIA), or implanted defibrillator or pacemaker (except for uncomplicated elective pacemaker procedure, 3 months post procedure will be allowed).
8. History of gastric bypass or bariatric surgery or planned procedure during the study period. Removal of a gastric balloon or lap band is permitted if surgery performed within 6 months prior to Day 1.
9. Type 1 diabetes

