iii. Adverse event of muscle symptoms (e.g., myalgia, pain, or weakness) or elevated creatine kinase:

A sample will be collected for assessment of CK within 48-72 hours, and CK assessment will be repeated if needed (refer to [Appendix 5](#)). At Weeks 12 and 24, the creatine kinase (CK) level will be compared to the subject's baseline level.

- If CK level is $\leq 3x$ baseline, subject will continue on aldafermin and over-encapsulated rosuvastatin.
- If CK level is $> 3x$ baseline, CK will be repeated within 48 - 72 hours and aldafermin and rosuvastatin will be held:
 - If CK is $\leq 3x$ baseline, subject can re-start on aldafermin and rosuvastatin based on the investigator's judgement.
 - If CK is $> 3x$ and $< 5x$ baseline, repeat CK levels within 48 - 72 hours while aldafermin and rosuvastatin on hold.
 - If CK is $\geq 5x$ baseline, aldafermin and rosuvastatin will be discontinued.

Upon repeat testing for subjects previously with CK $> 3x$ but $< 5x$ baseline:

- If CK is $\leq 3x$ baseline, subject can re-start on aldafermin and rosuvastatin based on the investigator's judgement.
- If CK level is $> 3x$ baseline, subject will discontinue aldafermin and rosuvastatin.

iv. Laboratory value(s) indicative of DILI:

- a) Elevation of AST or ALT $> 2x$ above subject-specific baseline value (calculated using the average of the Day -42, Day -28 and the Day 1 values) and total bilirubin $> 1.5 \times$ subject-specific baseline value, repeat testing of ALT, AST, and bilirubin must be performed within 48 - 72 hours. If there are persistent elevations (AST or ALT $> 2x$ baseline or TBL $> 1.5x$ baseline values) upon repeat testing, then close observation (testing and physical examination 2 - 3 times per week) should be implemented and discontinuation of aldafermin and rosuvastatin should be considered (see b [below](#)).
- b) A decision to discontinue or temporarily interrupt the study drug will be considered based on factors that include how much higher than baseline ALT and AST were relative to the upper limit of normal (ULN) and how much the on study ALT and AST levels have increased relative to baseline, in addition to whether there is concomitant elevation of bilirubin or INR. Aldafermin and rosuvastatin will be discontinued or temporarily interrupted as follows:
 - If baseline measurements (BLM) were $< 2x$ ULN, discontinue if ALT or AST increases to $> 5x$ BLM
 - If BLM $\geq 2x$ ULN but $< 5x$ ULN, discontinue if ALT or AST increases to $> 3x$ BLM

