9.4.9 Clinical Laboratory Evaluations

Clinical laboratory evaluations will be collected as outlined in [Table 4](#). Blood and tissue samples will be collected and any remaining or back-up study samples may be used for future exploratory and biomarker analysis related to aldafermin treatment or metabolic diseases. The samples will be stored for up to 15 years.

Serum chemistry will include ALT, AST, ALP, bicarbonate, bilirubin (direct and total), BUN, calcium, chloride, creatinine, CK, GGT, glucose, HDL, LDL, lipase, phosphate, potassium, proteins (albumin, total protein), sodium, total cholesterol, and TG. Creatine Kinase will be collected at Day -42, Day 1, Weeks 12 and 24. Samples for analysis of ADAs, NAbs, and exploratory biomarkers will be collected. A blood sample for genetic biomarker testing will be collected pre-dose on Day 1. All NAB samples will be collected as scheduled, and analyzed only if necessary, based on ADA results.

Liver function tests, including AST, ALT, TBL and ALP, will be compared between Day -42 and Day -28 to assess whether there is worsening of liver disease during screening according to exclusion criterion [#6](#). An unscheduled visit may be necessary to confirm eligibility if the difference exceeds 35%. If performed, unscheduled visit results will be compared to the average of Day -42 and Day -28 results to determine if eligibility ranges (i.e., % agreement $\leq 35\%$) are met.

Processing, storage, and shipping instructions for the above will be presented in a separate Lab Manual.

9.4.10 12-Lead Electrocardiograms

12-lead ECGs will be performed after the subject has been supine for at least 5 minutes, and as outlined in [Table 4](#).

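### The screening liver retest judges the third value against an average that contains the value in question, so a confirmed rise of up to about 108% passes a criterion whose own limit is 35%

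*Protocol*

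**What the plan says.** Protocol 8.2, criterion 6, excludes "Evidence of worsening liver disease (defined below) between Screening visits (i.e., Day -42 and Day -28"), for AST, ALT, total bilirubin and ALP. Two bullets define it. For values above ULN on Day -28, "the Day -28 assessment should not exceed an increase of 35% over the Day -42 assessment". For subjects with Gilbert's syndrome whose total bilirubin is above ULN at Day -42, the allowed rise in bilirubin is 50%.

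A Note then sets a retest. It opens "For AST, ALT, TBL, and ALP, if the percent increase in laboratory values between Day -42 and Day -28 is" above 35%, with no ULN condition and no Gilbert's exception. The repeat sample is "collected at an unscheduled visit at a minimum of two weeks from the Day -28 visit". The decision rule follows: "The average of Day -42 and Day -28 values will be compared to the 3rd value to determine if eligibility ranges" are met, glossed as % agreement of at most 35%.

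The synopsis carries the same Note ("The average of Day -42 and Day -28 values will be compared"). Section 9.4.9 repeats the comparator: "unscheduled visit results will be compared to the average of Day -42 and Day -28 results to determine if eligibility ranges" are met. It speaks of a difference exceeding 35% where 8.2 speaks of an increase. No section says whether agreement is one-sided or two-sided, or what the percentage is taken of.

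Screening values are used again in 8.3 iv a, where the subject-specific AST or ALT baseline is "calculated using the average of the Day -42, Day -28 and the Day 1 values".

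**The concern.** A retest after a suspicious rise should show whether the rise was real. The value under suspicion should not help set the standard by which it is judged. Here it makes up half of that standard and pulls the reference up towards itself, so a third sample that confirms the rise looks closer to acceptable than it is.

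The consequence is that subjects with a rise seen at Day -28 and confirmed at least two weeks later can be enrolled under a criterion written to exclude them. Criterion 6 is the only listed criterion that tests change between screening visits. The AST ceiling of 250 IU/L and the bilirubin limit in inclusion 7 test level, and there is no listed ceiling for ALT or ALP.

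**Working it through.** The plan gives no figure for how the retest performs, so there is nothing to reproduce. The inputs are the 35% limit and the two reference values in criterion 6.

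**Algebra.** Set Day -42 to 1 and Day -28 to 1 + r. The reference is the average, 1 + r/2. Take the percentage relative to that average.

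- Rise sustained (third value 1 + r): (1 + r)/(1 + r/2) - 1 = +r/(2 + r).
- Rise fully resolved (third value 1): 1/(1 + r/2) - 1 = -r/(2 + r).

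A sustained rise passes while r/(2 + r) ≤ 0.35, that is r ≤ 0.70/0.65 = 1.077. The effective limit after a retest is about 108% over Day -42, against the stated 35%.

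**Worked triples (ALT at Day -42, Day -28, retest).**

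| Values | Average of first two | Third vs average | Third vs Day -42 |
|---|---|---|---|
| 60, 120, 120 (sustained) | 90 | +33% | +100% |
| 60, 100, 108 (still rising) | 80 | +35% | +80% |
| 60, 120, 60 (resolved) | 90 | -33% | 0% |
| 60, 130, 60 (resolved) | 95 | -37% | 0% |

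The first two rows pass.

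**What agreement could mean.**

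- Absolute difference from the average: the two formulas differ only in sign, so a sustained and a fully resolved rise get the same verdict at every r. Both pass up to 108% and both fail above it. Row 4 is ineligible.
- Increase only: both pass up to 108%. Above that, the sustained rise fails and the resolved one passes. Row 4 is eligible.
- Absolute difference, third value as denominator: for a doubling, sustained is (120 - 90)/120 = 25% and passes; resolved is 30/60 = 50% and fails.
- Absolute difference, midpoint as denominator: sustained is 30/105 = 28.6% and passes; resolved is 30/75 = 40% and fails.

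A sustained doubling passes under all four.

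**Pass rates with measurement variation.** Assumptions: one analyte, independent log-normal variation, within-subject CV 15% (range 10-20%, not from the documents), 400,000 draws per case, ULN condition not applied. Rates are among subjects whose observed Day -28 rise exceeds 35%. The as-written column uses the absolute difference from the average; for the two sustained cases, increase-only gives practically the same rates.

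| True course | Passes as written | Passes if judged against Day -42, increase only |
|---|---|---|
| Sustained +75% | 65% (62-69) | 8% (3-13) |
| Sustained +100% | 54% (54-55) | 3% (0-6) |
| +75%, fully resolved | 71% (64-81); about 100% if increase-only | 91% (83-98) |

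**Effect on 8.3 iv a.** With 60 and 120 at screening and 120 on Day 1, the baseline is (60 + 120 + 120)/3 = 100. The AST/ALT arm of the repeat-test trigger, more than twice baseline, then means more than 200, or 3.33 times the Day -42 value. The trigger also requires a bilirubin rise.

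**The case against.** **The reading of agreement.** The criterion concerns worsening, and its bullets and trigger speak only of increases, so an increase-only reading is at least as natural as an absolute one. This stands. A reader might infer that the retest rejects subjects whose tests have settled, or that it can never separate a persistent rise from a resolved one. The documents do not fix the reading that either inference needs. Under increase-only, resolved spikes are not rejected and the two courses separate above 108%. The pass given to sustained rises up to 108% does not depend on this choice.

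**Averaging has a purpose.** Subjects sent to retest are partly selected for a Day -42 value that was low by chance, and averaging two values guards against regression to the mean. It is a fair reason to expect more false exclusions if Day -42 alone is the reference, and that cost is counted in the fix. It does not reconcile a 108% allowance with a 35% limit. A sponsor might say that the retest looks for a new plateau, but the criterion is written to exclude a rise between the two visits.

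**Downstream harm.** Two stronger readings tempt. One is that admitted subjects add noise to histology. Nothing in the documents shows this: the baseline biopsy may predate Screening by up to six months, and assignment is randomized. The analyses of ALT and AST change also adjust for baseline value. The other is that the 8.3 iv b discontinuation limits become laxer. Those multiples shrink as baseline rises. If ULN is 40 and the iv b baseline is the same average (both assumptions), a baseline of 100 gives a limit of 3 x 100 = 300 and a baseline of 60 gives 5 x 60 = 300. Only the iv a trigger scales directly.

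**Other safeguards.** The AST and bilirubin limits, MELD, investigator or Medical Monitor judgement under exclusion 25, and the Day 1 reassessment of criteria limit severity. None tests persistence.

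**Conclusion.** The point holds for sustained rises. Followed exactly, the Note admits subjects with a confirmed rise of up to about 108% over Day -42, where the criterion's own limit is 35%, and a sustained doubling passes under each of the four readings tested. The 108% figure is exact when the percentage is taken of the average. The pass rates of about 65% and 54% rest on the assumed CV and are conditional on a true sustained rise and a retest. The documents do not say how often such rises occur, so the effect on the trial as a whole is not quantified.

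The undefined agreement term is a second defect, and so is the mismatch between the Note's trigger and the bullets, which carry a ULN condition and a Gilbert's allowance that the Note lacks. The shown downstream effect is a higher baseline for the 8.3 iv a trigger.

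**What to change.** Reconcile the Note in the synopsis, 8.2 and 9.4.9 with the criterion's own bullets:

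- Judge the third value by the same test as the Day -28 value: same Day -42 reference, increases only, same ULN condition, same Gilbert's allowance for bilirubin. The triggering Day -28 value is not part of the reference.
- Put the same conditions on the retest trigger. Replacing only the comparator would exclude a Gilbert's subject stable at +40%, who meets the 50% bullet and passes the Note now (1.4/1.2 = +17%). It would also exclude bilirubin of 0.4, 0.6, 0.6, if all within normal, which passes now at +20% against the average but is +50% against Day -42.
- Define % agreement, or drop the term.

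Sampling, timing and the 35% figure stay as they are; no visit or test is added.

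The cost is more screen failures among truly stable subjects. At CV 15%, about 8% trigger a retest on a given analyte, and of those 71% rather than 95% pass: 0.08 x (0.95 - 0.71) = about 2% per analyte, and 0.3% to 3-4% over CV 10-20%. Over four analytes, if independent and all above ULN, the loss is up to 1 - (1 - 0.019)^4 = about 7% at CV 15%, and about 13% at CV 20% (1.9% and 3.4% per analyte). The ULN condition would lower this. If the Note is now applied as increase-only, resolved +75% spikes would pass about 91% of the time rather than nearly always.
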